### 11.5 Management of Toxicities

All local reactions will be considered causally related to administration of the suppositories. Causality of all other adverse events will be assessed individually. We will follow up subjects with non-serious adverse events until symptoms end. Those with

related serious adverse events will be followed until resolved, until no further improvement is expected, until a non-study antitumor therapy is initiated, or for 30 days after last study treatment, whichever comes first (with the exception of neuropathy, which must be followed until resolution to  $\leq$  grade 1 or until stable for 60 days).

Outcome will be assessed as

- 1=Recovered
- 2=Recovered with sequelae
- 3=Ongoing at subject study conclusion
- 4=Died
- 5=Unknown

Any serious study events that are unexpected and related to the study drug or procedure occurring during the period starting from day of administration of the first dose of Artesunate suppository to each subject and ending at the last study visit for that subject (i.e., scheduled LEEP or cone excisional biopsy procedure), will be reported by the principal investigator.

Subjects who become pregnant during study will be required to discontinue drug. Subjects removed from the study prior to week 15 will be replaced in the dose cohort. Although not considered an adverse event, pregnancy will be reported in the same way. Whenever possible, a pregnancy should be followed to term, and the status of mother and child reported. The Pregnancy Notification form will be sent by sites to the study sponsor ([name]) within 48 hours of discovery. Whenever possible, the Follow-up Pregnancy Outcome Form will be filled after delivery.

Significant local inflammation will be treated symptomatically with cold packs and oral analgesics. Local infection or ulceration will be treated with routine wound care and antibiotics if necessary.

Subjects will be given diary cards to record local and general signs and symptoms most likely to occur at home. The diary cards will be collected, signs and symptoms verified, and inserted into the CRF at each subsequent visit. Subjects will be monitored at regular intervals to ensure that all adverse events are recognized, documented, and treated. Patients will be educated to contact medical staff should they feel that an adverse event has occurred at a time when they are not scheduled for follow-up monitoring and will have access to medical staff to follow up on any such concerns.

All unexpected and related SAEs will be reported immediately to [name], who will remove any at-risk patient from the study. Any subject who shows evidence of a drug-related SAE (grade III or IV) will be removed from the study and the SAE will be reported to the FDA and the JHMIRB within 7 working days of finding out.

Risks to privacy of individuals, confidentiality of data: There is a potential risk of loss of confidentiality. To ensure that all information and specimens collection remain

confidential and anonymous, all study data will be de-identified. Only the research team will have access to study participant private data. All study specimens are de-identified and cannot be linked to the subjects. Specimens will be barcoded before storage so that patient identifiers will not be available to the laboratories performing the assays proposed in this application.

To ensure that all study data remains confidential, all study data will be maintained on a password-protected database. Patient identifying information will not be associated with the study research data. Only the research investigators will be able to access a list connecting patient identifiers with the study ID, and this can only be provided upon special request from the study database managers.

The rate at which invasive cancer develops from CIN is slow and can take years and perhaps decades [49]. The fifteen-week treatment study window precedes the standard LEEP or cone excisional biopsy procedure given to the targeted study population, and therefore will not extend the normal time clinicians allow between disease detection and therapy and as such, participation in this study will not affect optimal patient treatment.

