**Table 4 – Treatment Cohorts**

Cohort	Number of patients	Dose	Treatment cycles
I	3	50 mg	1 (5 days)
II	9	200 mg	1 (5 days)
III	9	200 mg	2 (5 days each)
IV	9	200 mg	3 (5 days each)

In cohort I, at the first study visit, the subjects will be given a total of five suppositories and applicators. The first suppository will be inserted in clinic, by the patient. Patients will be given diary cards, and will return 1-2 weeks after completing the regimen, for visual assessment of the cervicovaginal mucosa.

In cohorts II-IV, the first study visit will be the same as the first study visit for the run-in cohort. Subjects will return to clinic 1-2 weeks later for visual assessment of the cervicovaginal mucosa. At study week 2, patients enrolled in cohorts III and IV will undergo a visual assessment of their cervicovaginal mucosa and will be given an additional 5 suppositories and applicators. Patients enrolled in cohort III will return to clinic 1-2 weeks later for visual assessment of the cervicovaginal mucosa. At study week 4, subjects enrolled in cohort IV will undergo a visual assessment of their cervicovaginal mucosa, and will also be given five suppositories and applicators. At study week 6, **all subjects** will undergo an interval colposcopic assessment. If their lesions do not appear to be more severe than at study entry, they will return at study week 15. At study weeks 15 and 28, all subjects will undergo colposcopic evaluation. If there is any residual colposcopically abnormal tissue, it will be removed using standard excisional procedures. Peripheral blood and cervical brush specimens will be obtained at study entry, at week 5, at week 15, and at the follow-up visits: postoperative visit, and at weeks 28 and 41.

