#### **11.6 Definition of a Serious Adverse Event**

A serious adverse event or reaction is any untoward medical occurrence that at any dose:

- results in death
- is life-threatening (an event in which the subject is at risk of death at the time of the event; it does not refer to an event which hypothetically might have caused death if it were more serious)
- requires inpatient hospitalization or prolongation of existing hospitalization
- results in persistent or significant disability or incapacity
- is a birth defect/congenital anomaly

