### **11.8 Definition of Dose-Limiting Toxicity**

A dose-limiting toxicity is defined as any grade 3 toxicity in any organ system, or grade 2 or higher allergic reaction/hypersensitivity reaction (allergy/immunology), as delineated in CTCv4.0.

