### **11.9 Early stopping rules**

Because this is a pilot study evaluating tolerability of a new intra-vaginal treatment, the stopping rule for safety is the presence of Grade 3 toxicity in any organ system, or grade 2 or higher allergic/hypersensitivity reaction as delineated in CTCAEv4.0. In the event of two identical unexpected related treatment-related Grade 3 toxicities, accrual will be suspended pending further review.

Subjects who become pregnant during study will be required to discontinue drug. Although not considered an adverse event, pregnancy will be reported in the same way. Whenever possible, a pregnancy should be followed to term, and the status of mother and child reported. The Pregnancy Notification form will be sent by sites to the study sponsor ([name]) within 48 hours of discovery. Whenever possible, the Follow-up Pregnancy Outcome Form will be filled after delivery.

Finally, if there is evidence of disease progression at the interval visit regardless whether the progression may or may not be associated with Artesunate, patients will undergo resection at that point.

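### The protocol does not say clearly what a non-serious dose-limiting toxicity means for a woman's further cycles, and Section 11.5 merges stopping drug with leaving the study

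*Combined protocol and SAP*

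**What the plan says.** All references are to the combined protocol and SAP.

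- **Removal for toxicity (11.5).** "Any subject who shows evidence of a drug-related SAE (grade III or IV) will be removed from the study". The same section lets an at-risk patient be removed after an unexpected, related SAE. For pregnancy it says: "Subjects who become pregnant during study will be required to discontinue drug".
- **SAE (11.6).** Defined by outcome: death, threat to life, disability, birth defect, or an event that "requires inpatient hospitalization or prolongation of existing hospitalization".
- **DLT (11.8).** Defined by grade: "any grade 3 toxicity in any organ system, or grade 2 or higher allergic reaction/hypersensitivity reaction". Neither seriousness nor causality is required.
- **Stopping rule (11.9).** "the stopping rule for safety is the presence of Grade 3 toxicity in any organ system", with the same allergy criterion as 11.8. A separate sentence suspends accrual after two grade 3 events of the same kind that are unexpected and related.
- **Escalation (12.1).** One DLT among nine women leads to three more women at that level.
- **Dispensing (10.3, 11.2 to 11.4).** For the week 2 visit the text reads: "patients enrolled in cohorts III and IV will undergo a visual assessment of their cervicovaginal mucosa and will be given an additional 5 suppositories". Cohort IV has the same sequence at week 4. A negative pregnancy test is the one condition stated for handing over a cycle.
- **After removal.** Women removed before week 15 are replaced (11.5; dropouts also in 12.1 and 13.1). Follow-up of a related SAE stops no later than 30 days after last treatment, except for neuropathy (11.5).
- **Use of week 15.** Viral load and lesion clearance at week 15 guide the choice of the expansion level (12.1).

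**The concern.** Two things are at stake.

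The first is the individual woman in cohort III or IV who has a DLT that is not an SAE. The clearest example is a grade 2 allergic reaction, which in Table 5 includes urticaria and dyspnea. Section 3.1 names type 1 hypersensitivity as the one potentially serious effect convincingly tied to this drug class, so this is the event on which the text should be plainest. The trial has two clinical sites, and they could treat the same event differently while each believes it is following the protocol.

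The second is the week-15 data. If a toxicity takes a woman out of the study and not just off the drug, and another woman fills her place, the cohort on which activity is judged is partly selected for tolerating the drug.

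**Working it through.** **1. The rules side by side.**

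| Event, managed without admission unless stated | DLT (11.8) | SAE (11.6) | Action in 11.5 | Criteria of 11.9 | Bar to next cycle in 10.3/11.4 |
|---|---|---|---|---|---|
| Grade 2 allergic reaction | yes | no | none stated | met; what stops is not stated | none stated |
| Grade 3 local reaction | yes | no | unclear: not an SAE, but within the grades in the parenthesis | met; what stops is not stated | none stated |
| Grade 3 drug-related event with admission | yes | yes | leaves the study | met; what stops is not stated | none stated |

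The first row lies outside 11.5 even if its parenthesis is read generously.

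**2. The two readings of 11.9.**

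- *It stops the woman.* It then contradicts 11.5 on threshold (grade against SAE) and on causality (none required against drug-related).
- *It stops the trial or cohort.* It then contradicts 12.1, where one DLT in nine adds three women, and its own accrual clause, which needs two matching events. The plan's maximum for escalation confirms that it expects to continue after one DLT at each of levels II to IV: 3 + 3 × (9 + 3) = 39, the figure stated in 12.1.

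Neither reading removes the need to reconcile.

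**3. Doses left.** Each cycle has 5 doses. After a DLT in cycle 1, 1 × 5 = 5 remain in cohort III and 2 × 5 = 10 in cohort IV. After a DLT in cycle 2 of cohort IV, 5 remain. The text governs 9 + 9 = 18 of the 30 planned women, plus the 12 expansion women if level III or IV is chosen. These are the women scheduled for a further cycle, not the number expected to be affected.

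**4. Can safety follow-up supply the week-15 data?** Take the latest case, cohort IV.

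- Nominal: the third cycle starts at week 4 (day 28) and the fifth daily dose is on day 32. 32 + 30 = day 62, about week 9.
- With the Section 10.2 windows, assuming that the allowance of up to 2 weeks for the remaining doses applies to this cycle: start at week 5 (day 35), last dose on day 49. 49 + 30 = day 79, about week 11.
- The earliest week-15 visit is week 14, day 98. The gap is 98 − 79 = 19 days.

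A woman removed earlier has an earlier cut-off. Except for neuropathy, the follow-up described for a removed woman therefore ends before the week-15 histology and viral load.

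**5. How often could the dosing gap arise?** The documents give no rate, and Section 5.0 expects no DLTs, so this is an illustration. Let q be an assumed per-cycle probability of a non-serious DLT, independent across women and cycles. The chance that at least one of nine women has such a DLT before a further scheduled cycle is 1 − (1 − q)^9 in cohort III and 1 − (1 − q)^18 in cohort IV.

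| q | Cohort III | Cohort IV |
|---|---|---|
| 1% | 9% | 17% |
| 5% | 37% | 60% |
| 10% | 61% | 85% |
| 20% | 87% | 98% |

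**The case against.** The strongest defence is Section 11.9. It uses the DLT criteria exactly, the paragraphs after it concern individuals (pregnancy, progression), and reading it for the trial creates two contradictions. The individual reading is therefore at least as coherent, and under it the woman in question stops. Section 13.3 also foresees leaving for a non-serious adverse event, and Section 11.3 requires a drug order, so an investigator can withhold a cycle.

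This defeats several stronger readings that a reader might infer:

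- *That the plan directs sites to dispense the next cycle after a DLT.* It does not. The gap is silence and conflict, not an instruction to re-dose.
- *That a drug-related SAE is the sole event ending dosing.* Pregnancy also ends it, and a site could apply the parenthesis in 11.5 to related grade 3 and 4 events. Section 11.5 deems all local reactions related.
- *That pregnancy is a precedent for staying in follow-up.* No section says that pregnant women keep their scheduled visits.
- *That each removal shrinks the week-15 data of a nine-woman cohort.* Replacement refills the cohort. The issue is its composition, not its size.
- *That women with strong local reactions generally leave before week 15.* Selection is confined to those actually removed under 11.5, and Section 3.2 anticipates no serious events.

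What the defence does not remove: 11.9 never says what stops; the dispensing text does not refer to 11.8 or 11.9; and a reason code on a case report form is not a dosing rule. Efficacy is secondary and mainly descriptive, but it still guides the choice of the expansion level.

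**Conclusion.** The concern holds as an inconsistency across Sections 10.3, 11.4, 11.5, 11.6, 11.8, 11.9 and 12.1. A site following 10.3, 11.4 and 11.5 has no clear instruction against a further cycle of 5 or 10 doses after a non-serious DLT. Either reading of 11.9 contradicts another part of the protocol.

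The second part also holds, by inference. Loss of the week-15 result is not stated. It follows from removal, replacement, event follow-up that ends by about week 11, and the absence of any text retaining her.

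The size is uncertain on both counts. The frequencies above rest on assumed rates, and the number removed under 11.5 may be none or very few. The point merits correction because the trial is small, safety is its primary outcome, and the remedy is cheap.

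**What to change.** 1. The sponsor and investigators should reconcile the sections listed in the verdict so that the reader can tell which event definition governs an individual's further cycles and which governs the cohort or trial. The dispensing text for weeks 2 and 4 should refer to whichever definition they settle on. No threshold or clinical rule is proposed here.
2. State in 11.5 that ending study drug does not end follow-up. Unless she withdraws consent, the woman keeps the remaining scheduled assessments, including week 15.
3. State in 12.1 and 13.1 that her week-15 result is reported in her assigned cohort, and that any replacement is reported in addition to her and not in her place.

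The cost is protocol wording and a few more follow-up visits for women who stop the drug. Those visits are already in the schedule.

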#### **11.6 Definition of a Serious Adverse Event**

A serious adverse event or reaction is any untoward medical occurrence that at any dose:

- results in death
- is life-threatening (an event in which the subject is at risk of death at the time of the event; it does not refer to an event which hypothetically might have caused death if it were more serious)
- requires inpatient hospitalization or prolongation of existing hospitalization
- results in persistent or significant disability or incapacity
- is a birth defect/congenital anomaly

#### **11.7 Recording and Follow-up of Adverse Events**

The severity of each adverse event must be assessed using the NCI Common Terminology Criteria for Adverse Events, v4.0 (CTCAE 4.0).

All adverse events that occur from the time of study drug administration through 30 days after the final treatment will be recorded. Duration, severity, treatments administered and outcome for each adverse event will be recorded on the CRF for the following visit. Drug related adverse events will be followed until resolved, until no further improvement is expected, until a non-study antitumor therapy is initiated, or for 30 days after last study treatment, whichever comes first (with the exception of neuropathy, which must be followed until resolution to  $\leq$  grade 1 or until stable for 60 days).

Adverse events beginning 30 days after the last treatment that the investigator considers to be related to study treatment will be reported to the appropriate contact person at any time such events occur.

Conditions that were present at the study start and that worsen during the study should be reported as beginning on the date the event worsened, not the date it began pre-study. Event text may include the word “worsened” or “exacerbated.”

Conditions which were recorded as “intermittent” at the study start which occur during the study must be reported if they are more frequent or of greater severity.

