## **4.0 OVERALL ASSESSMENT OF RISKS AND POTENTIAL BENEFITS**

### **4.1 Potential Risks**

The major risks for the study subjects are associated with surgical excision procedures that are the standard of care for patients with CIN2/3. Other potential risks posed by this clinical protocol would include local tissue irritation due to the presence of the investigational drug, and venipuncture for peripheral blood collection.

Intra-vaginal administration of Artesunate suppositories has not been approved for general use by the Food and Drug Administration (FDA). An Investigational New Drug (IND) application covering the proposed was submitted to the FDA. Approval to conduct this clinical trial was obtained from the FDA before clinical enrollment began. The IND governing this protocol is IND 124299. In parallel, the clinical trial protocol

was reviewed and approved by the Johns Hopkins Hospital Institutional Review Board, and the Johns Hopkins Cancer Center Clinical Research Committee.

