**Table 3: Outline of Evaluation Procedures**

	-3wks	Wk 0	Wk 2 	Wk 4 	Wk 6	Wk 15	Postop **	Wk 28	Wk 41
Informed consent	X								
Artesunate dosing		X	X	X					
Vital signs	X	X	X	X	X	X	X	X	X
Cervix check			X	X	X	X			
Medical history	X								
History of disease	X								
Demographic data	X								
Diary cards (give to pt)		X	X	X		X			
Diary cards (collect from pt)			X	X		X			
Adverse events		X	X	X	X	X	X	X	X
Inclusion/exclusion criteria	X								
Colposcopy	X				X	X		X	(X)*
Pap smear	X				X	X		X	X
HPV genotyping	X				X	X		X	X
Cervical swabs	X	X	X	X	X	X	X	X	X
LEEP/Cone**						(x)		(x)	
HLA testing ***	X								
PBL for banking****	X	(X)			X	X	X	X	X
Urine HCG	X	X	X	X		X			
Optional pheresis*****									

1. Treatment Group III

2. Treatment Group IV

\* Colposcopy only if clinically-required at wk 41

\*\* if residual disease is present (the procedure can happen any time after week 15, based on the physician's clinical judgment). The Postoperative visit will take place 4 +/- 1 weeks after the LEEP/Cone procedure.

\*\*\* HLA can be done at any time during the study, not an eligibility criterion

\*\*\*\* First blood draw can be done at either the screening visit or Wk 0, prior to dosing

\*\*\*\*\* pheresis is optional and can happen any time after week 15

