We will correlate immune response with clinical response by looking at the association with disease regression. A logistic regression analysis will be performed with regression as the outcome and baseline and change between baseline and follow-up HPV viral load as predictors, where HPV viral load and the change have been transformed for normality. Using these two predictors, we can assess how change in viral load is associated with clinical response, adjusting for baseline level. Other predictors of interest will also be evaluated, including measures of E7-specific immune response. To explore the association between continuous outcomes of interest and time, the random effects model described above will be used.

The frequency and severity of all toxicities will be tabulated from CRFs and summarized for review in a descriptive fashion. The initial review of toxicity will be completed after the first treatment group has completed the intervention portion of the study (through week 5).

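### AE windows in 11.5, 11.7 and Table 3 differ, and the open-ended rule on local reactions lets excision effects be tabulated as suppository toxicity

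*Combined protocol and SAP*

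**What the plan says.** Three passages set an end to AE collection or reporting, and they differ.

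- Section 11.7: "All adverse events that occur from the time of study drug administration through 30 days after the final treatment will be recorded". A later clause keeps a narrower route open: "Adverse events beginning 30 days after the last treatment that the investigator considers to be related to study treatment will be reported", at whatever time they occur.
- Table 3: the row "Adverse events" is marked at weeks 0, 2, 4, 6 and 15, the postoperative visit, and weeks 28 and 41. No footnote limits it to related events. On timing, "The Postoperative visit will take place 4 +/- 1 weeks after the LEEP/Cone procedure".
- Section 11.5: the period for reporting serious, unexpected, related events is described as "ending at the last study visit for that subject (i.e., scheduled LEEP or cone excisional biopsy procedure", although Table 3 schedules visits after that procedure.

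On causality, 11.5 says: "All local reactions will be considered causally related to administration of the suppositories". All other events are assessed one by one. The term local reaction is not defined, the rule has no end date, and biopsy and excision are not exempted.

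On analysis, 12.4 says: "The frequency and severity of all toxicities will be tabulated from CRFs and summarized for review in a descriptive fashion". Section 4.1 is explicit about where the risk lies: "The major risks for the study subjects are associated with surgical excision procedures that are the standard of care for patients with CIN2/3".

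**The concern.** Safety is the primary outcome, and there is no concurrent control group to show how much local pain or bleeding surgery alone produces. The excision is done at the site where the drug is applied. Pain, infection and bleeding are among the events that 7.1 names for the safety assessment. An event caused by the LEEP/cone can therefore look like a local reaction to the suppository, and 11.5 then supplies the causality without anyone having to judge it.

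Two things are at stake. First, staff following 11.7 and staff following Table 3 would hold different sets of late events. Second, the distortion is tied to efficacy: a cohort with fewer regressions has more excisions, and so more apparent local toxicity. Section 12.1 lets the choice of expansion dose rest on the overall safety and efficacy profile when no dose reaches significance, so the summary could bear on a decision.

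**Working it through.** The plan gives no figure to reproduce here. The check is date arithmetic on the windows, followed by tracing how an excision event would reach the table.

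**Inputs.** Cycles start on day 0, week 2 (day 14) and week 4 (day 28) (Synopsis, Study Design). The four remaining doses of a cycle take from 4 days to 2 weeks, and visits at weeks 2, 4, 6 and 15 may move by 1 week (10.2). Week 6 is day 42 (range 35 to 49), week 15 is day 105 (range 98 to 112), and week 41 is 41 × 7 = day 287.

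**Formulas.** Nominal end of the 30-day window = start of last cycle + 4 + 30. Latest end = start of last cycle, plus 7 if that cycle is not the first, + 14 + 30. The latest case assumes that the 2-week allowance applies to every cycle.

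| Cohort | Nominal end | Latest end | Gap to week 15, nominal | Gap, tightest | Table 3 continues for |
|---|---|---|---|---|---|
| I, II | 0+4+30 = 34 | 0+14+30 = 44 | 105−34 = 71 | 98−44 = 54 | 287−34 = 253 |
| III | 14+4+30 = 48 | 21+14+30 = 65 | 105−48 = 57 | 98−65 = 33 | 287−48 = 239 |
| IV | 28+4+30 = 62 | 35+14+30 = 79 | 105−62 = 43 | 98−79 = 19 | 287−62 = 225 |

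All entries are in days.

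**Excision at week 15 or later.** It falls outside the all-AE window of 11.7 in every cohort. Its effects can reach the CRF by two routes: the unrestricted AE row of Table 3, or the late related-event clause of 11.7. If a surgical effect counts as a local reaction, the rule in 11.5 makes it related and so satisfies that clause.

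**Excision at the interval visit.** Section 11.9 provides for resection if disease has progressed at that visit, which 5.0 places at week 6. Day 42 lies inside the 30-day window for Cohorts III (ends day 48) and IV (ends day 62) on the nominal schedule, and for Cohorts I and II only if the cycle is prolonged (ends day 44 at the latest). Here 11.7 records the surgical event directly, so a 30-day limit alone would not remove the problem.

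**Tabulation.** Section 12.4 counts whatever is on the CRF and has no split at excision.

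**Escalation.** Under 12.1, DLTs count up to the cervix check after the last suppository, which precedes week 15. Step 5 (Cohort III) does not repeat that limit; I read it as the same.

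**The case against.** The case on the other side has four parts.

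- **The late clause partly reconciles the sections.** Asking about AEs at weeks 15, 28 and 41 is how late related events would be found. This stands for related events. For unrelated events after 30 days, Table 3 and 11.7 still disagree.
- **Local reaction may simply mean a reaction to the suppository.** Surgical effects would then be other events, assessed individually, and the late clause does keep the investigator's judgement. This is a natural reading, but the text does not state it. Misattribution is therefore possible, not certain.
- **The effect on decisions is limited.** The tabulation is descriptive, and the initial toxicity review covers the first group only through week 5. Visit columns in Table 3 would let an analyst separate most events afterwards. All of this stands, but nothing in the plan requires the separation.
- **Automatic attribution is a cautious choice for a new route of administration.** Agreed while the drug is being given and shortly afterwards. It protects nobody once it absorbs the effects of surgery.

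A reader might go further and put a number on the problem: with 20-25% regression, 30 × 0.75 = 22.5 to 30 × 0.80 = 24 women are excised, so 75-80% could carry a surgical event labelled related. The documents do not support this. The rate in 5.0 is for HPV16-associated lesions; the same section says other genotypes are more likely to regress, and 9.1 admits any HPV-positive woman. Excision is triggered by a colposcopic lesion, whereas regression is judged on histology, so one minus the regression rate is not the excision rate. The denominator is unsettled too: the Synopsis gives 30, while 12.1 gives up to 39 in escalation and 12 in expansion. No rate of recorded pain or bleeding after excision is given.

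**Conclusion.** The point holds as a gap between stated rules. Followed as written, 11.5, 11.7, 12.4 and Table 3 allow pain, bleeding or infection from an excision to be counted as drug-related local toxicity in the summary of the primary outcome. The size that can be given is in time: AE collection under Table 3 outlasts the 30-day window by 225 to 253 days on the nominal schedule, and that window closes at least 19 days before the earliest week-15 visit. How many women would be affected cannot be derived.

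The conclusion rests on local reaction being undefined and on the Table 3 row applying as marked. A reader might also infer that dose escalation is biased. For week-15 surgery it is not, because DLTs stop counting earlier. Separately, the first sentence of the stopping rule in 11.9 carries neither a time window nor a relatedness condition, so whether it reaches post-excision events should be settled when these sections are reconciled.

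**What to change.** 1. Reconcile 11.5, 11.7 and Table 3 to one AE collection window, and footnote the Table 3 row to match.
2. Define local reaction in 11.5. Apply automatic causality only to local reactions with onset from first dose to 30 days after last dose and before any LEEP/cone. Both limits are needed because of resections at the interval visit.
3. In 12.4, tabulate events in that period as the main toxicity table. Show later events and all post-excision events in a second table, with causality assessed individually. Discard none.

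The cost is wording and one extra table. The downside is that a late local effect of the drug would be recognised only through individual causality assessment; showing the second table in full limits that loss.
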